6.1 Treatment Schedule

Lenalidomide capsules will be taken orally in the morning each day on days 1 - 21, followed by 7 days of no therapy of each 28-day cycle. Rituximab will be given by intravenous infusion weekly for 4 weeks beginning on day 15 of treatment start, thus on days 15, 22 of cycle 1 and days 1 and 8 of cycle 2.

Following cycle one, therapy with lenalidomide will continue in 28-day cycles, until there is disease progression, unacceptable toxicity or the patient chooses to withdraw from therapy. Lenalidomide may be discontinued after twelve cycles if complete response demonstrated, per physician and patient discretion. Additional course of rituximab will be administered if CR not attained after cycle 4, to be administered during cycle 5 on days 1, 8, 15 and 22. The patient must see the study physician before the next cycle may begin. There will be a +/-3 day window for study visits and procedures after completion of cycle one.

Dosing regimen

The planned maximum dose of lenalidomide for investigation is 20 mg daily, days 1-21 of a 28 day cycle. Dosing will be in the morning at approximately the same time each day. Lenalidomide may be taken orally either with a full or an empty stomach.

Due to the uncertain amount of re-absorption of lenalidomide, there will be no re-dose for lenalidomide if the patient vomits the pills.

Lenalidomide capsules should be swallowed whole, and should not be broken, chewed or opened.

If a dose of lenalidomide is missed, it should be taken as soon as possible on the same day. If it is missed for the entire day, it should not be made up.

Patients who take more than the prescribed dose of lenalidomide should be instructed to seek emergency medical care if needed and contact study staff immediately.

Prophylactic anti-coagulation is required during lenalidomide treatment. See Section 6.5.1.2.

Rituximab 375 mg/m2/week will be administered by IV infusion starting on day 15 from start of treatment and will continue weekly for 4 weeks (a total of four doses). The course of rituximab will be repeated if CR not attained after cycle 4. It will be administered at 375 mg/m2 weekly during cycle 5 on days 1, 8, 15 and 22.

For patients with peripheral blood involvement (leukemic presentation) as defined for this purpose as >20,000 lymphocytes per mm³ as determined by flow cytometry studies, the initiation of rituximab should be delayed until the lymphocyte count drops to <20,000/mm³ in the peripheral blood. For such patients, or for those with high tumor burden, despite lymphocyte count <20,000 cells/mm³ (as determined by the principal investigator), the infusion of rituximab may be divided as outlined below:

- Day 1 Rituximab 50 mg/m²
- Day 2 If no cytokine release phenomenon is noted on Day 1 of rituximab and the peripheral blood white cell counts have decreased to < 20,000 cells/mm³ or <25% of baseline WBC counts, then the dose of rituximab can be increased to 325 mg/m² on Day 2 at the PI discretion.

A similar 2-day split dose approach may be taken for rituximab infusion on subsequent dose of rituximab in patients with high tumor burden or high peripheral blood WBC counts as determined by the PI prior to each infusion of rituximab.

Pre-medication consisting of acetaminophen and diphendydramine should be considered before each infusion of rituximab to attenuate potential infusion reactions. Since transient hypotension may occur during rituximab infusion, consideration should be given to withholding antihypertensive medications 12 hours prior to rituximab infusion.

Rituximab First Infusion: The rituximab solution for infusion should be administered intravenously at an initial rate of 50 mg/hr. Rituximab should not be mixed or diluted with other drugs. If hypersensitivity or infusion related events do not occur, the infusion can be escalated to 50 mg/hr increments every 30 minutes, to a maximum of 400 mg/hr. If hypersensitivity or an infusion-related event develops, the infusion should be temporarily slowed or interrupted. The infusion can continue at one-half the previous rate upon improvement of patient symptoms.

Subsequent Rituximab Infusions: Subsequent rituximab infusions can be administered at an initial rate of 100 mg/hr, and increased by 100 mg/hr increments at 30 minute intervals, to a maximum of 400 mg/hr as tolerated.

Route of Administration

Rituximab is administered intravenously. To prevent infusion related or hypersensitivity events, rituximab is not to be administered as an intravenous push or bolus.

Please refer to rituximab package insert for details concerning drug storage, preparation and administration guidelines.

Subjects experiencing adverse events may need study treatment modifications (See section 6.4).

6.2 Special Handling Instructions

Females of childbearing potential **should not** handle or administer lenalidomide unless they are wearing gloves.

6.3 Record of administration

Accurate records will be kept of all study drug administration (including dispensing and dosing) will be made in the source documents.

To monitor treatment compliance, reconciliation of lenalidomide capsules will be done at each visit. Subject diaries will be provided to assist in the collection of dosing information to monitor compliance.

6.4 Dose Continuation, Modification and Interruption

Subjects will be evaluated for AEs at each visit with the NCI CTCAE v4.0 (Appendix III: NCI CTCAE v4.0) used as a guide for the grading of severity. Refer to Sections 6.5.1, 6.5.2 and 6.5.3 for full instruction on initiation of a new cycle of therapy and dose modifications during a cycle of therapy.

6.4.1 Lenalidomide Dose Reduction Steps

Lenalidomide will be initiated at a dose of 20 mg daily for 21 days on a 28 day cycle, except patients with renal insufficiency, who will start at a lower dose, as above.

Rituximab: There will be no dose reduction for rituximab. The rate of administration may be slowed or divided as needed based on tolerability. Patients with unacceptable hypersensitivity to rituximab will not receive further rituximab therapy.

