Response rate (overall and complete) in non-target lesions following local radiation with concurrent lenalidomide in patients previously refractory to the combination of lenalidomide and rituximab.

STUDY DESIGN:

The study will be a multi-institution, phase II clinical trial in patients with previously untreated indolent Non-Hodgkin's lymphoma. Patients will receive lenalidomide 20 mg daily, on days 1-21 of a 28 day cycle. Rituximab 375 mg/m2 will be administered weekly for 4 doses starting day 15 of cycle 1, to be repeated if patient does not achieve a complete response after cycle 4, on days 1, 8, 15 and 22 of cycle 5. Therapy with lenalidomide may be discontinued after twelve cycles if the patient achieves a complete response.

Patients progressing on lenalidomide and rituximab will be offered treatment in a radiotherapy cohort. Patients will continue lenalidomide at the current dose, on days 1-21 of a 28 day cycle. Local fractionated radiotherapy will be delivered to a single site of disease days 1-5 of a 28 day

cycle to 20 Gy in 4 Gy fractions. Re-staging will be performed every 2 months, and lenalidomide will be continued until disease progression or intolerance.

STUDY ENDPOINTS:

Primary:

Complete response (CR), near complete response (CRu), or partial response (PR), stable disease (SD) of 4 months.

Secondary:

Time to disease progression, tolerability, duration of response, overall survival, and tumor control rate from the start of treatment.

Measurement of immune profile

STUDY DURATION:	TOTAL SAMPLE SIZE:
Patients will be enrolled over 2yrs.	Approximately 30 patients
	Of the 30 total patients 10 progressing patients will be offered optional treatment on the radiotherapy arm
DOSING REGIMEN(S):	STUDY DRUG SUPPLIES:
Lenalidomide will be initiated at 20 mg daily, days 1-21 of a 28 day cycle, to be continued until disease progression, unacceptable toxicity or after twelve cycles if the patient has achieved a complete response. Rituximab 375 mg/m2/wk x 4 weeks, to begin Day 15 of cycle 1. After 4 cycles of therapy if patient	Celgene Corporation will supply lenalidomide as 5 mg capsules.
does not achieve CR, the patient will receive a second course of Rituximab.	
Blood samples for companion study to assess immune profiles will be obtained within 1 week	
prior to starting treatment & then on days 15, 30,	
60 and 120, and then at the end of treatment or	

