5.3 Overall design

The study is a phase II clinical trial with all patients to be accrued at UCD Cancer Center and other participating centers. All patients who are eligible will receive both lenalidomide and rituximab.

- Lenalidomide will be started at 20 mg daily, days 1-21 of a 28 day cycle.
- A total of 30 patients will be evaluated in this study.
- Rituximab 375 mg/m2/wk x 4 weeks, to begin on day 15 of cycle 1. After 4 cycles of therapy if a patient has not achieved a CR, the patient will be given a second course of Rituximab, on days 1, 8, 15 and 22 of cycle 5.

Patients who progress through this combination will be offered optional participation in a radiotherapy cohort. Up to 10 patients who consent will continue lenalidomide and receive local radiotherapy to a single target lesion.

- Lenalidomide will be continued at the patient's most recent dose daily, days 1 21 of a 28 day cycle.
- Radiotherapy will be delivered to a single involved site to a dose of 20 Gy over 5 daily fractions of 4 Gy each, day 1-5, using electron or photon beams with a conventional linear accelerator.

Investigational Drugs

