5.4.1 Inclusion Criteria

Subjects must meet the following inclusion criteria to be eligible for the study. (All responses to inclusion criteria should be YES)

- 1. All patients must be informed of the investigative nature of the clinical trial and give written informed consent in accordance with institutional and federal guidelines.
- 2. Age \geq 18 years at the time of signing the informed consent form.
- 3. Able to adhere to the study visit schedule and other protocol requirements.
- 4. Previously untreated, histologically confirmed indolent lymphoma including follicle cell lymphoma, WHO classification, grade I or II, and marginal zone lymphoma. Bone

marrow biopsies as the sole means of diagnosis are not acceptable, but they may be submitted in conjunction with nodal biopsies. Fine needle aspirates are not acceptable.

- 5. At least one measurable lesion according to the International Working Group Response criteria for lymphomas. There must be measurable lymphadenopathy to follow with serial exam and/or imaging.
- 6. Submission of original biopsy for review by hematopathologist at local institution.
- 7. ECOG performance status of 0 -2 at study entry. (see appendix II)
- 8. No major organ dysfunction with laboratory test results within these ranges:
 - Absolute neutrophil count $\geq 1000 / \text{uL}$
 - Platelet count $\geq 75 \times 10^9/L$
 - Total bilirubin $\leq 2.0 \text{ mg/dL}$.
 - HIV negative
 - Subjects must have calculated creatinine clearance ≥ 30ml/min by Cockcroft-Gault formula. See section below, "Dosing Regimen", regarding lenalidomide dose adjustment for calculated creatinine clearance ≥ 30ml/min and < 60ml/min.
- 9. Life expectancy of greater than 3 months.
- 10. All study participants must be registered into the mandatory Revlimid REMSTM program, and be willing and able to comply with the requirements of Revlimid REMSTM

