5.5 Visit schedule and assessments

Screening Assessments and all on study scheduled visits and assessments are outlined in Section 2 Table of Study Assessments.

An unscheduled visit can occur at any time during the study. Source must be maintained for these unscheduled visits. The date for the visit and any data generated must be recorded on the appropriate CRF. Source documents for these unscheduled visits must also be maintained.

At treatment discontinuation, subjects will undergo off study evaluations per the Schedule of Assessments, Section 2. In addition, a safety assessment will be done approximately 30 days post the last dose of study drug. Follow-Up contact with the subjects should occur at a minimum of 4 weeks.

If the subject is in remission for more than 1 year then follow-up will be every four months unless there are clinical indications.

6 Treatment assignments

All patients will receive the treatment regimen outlined below.

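### The protocol promises a lower lenalidomide starting dose for eligible patients with reduced renal function but never states it, and other sections start all patients at 20 mg without exception

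*Combined protocol and SAP*

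**What the plan says.** Two places promise a renal adjustment:

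- **Section 5.4.1, criterion 8.** "Subjects must have calculated creatinine clearance ≥ 30ml/min by Cockcroft-Gault formula". The same item sends the reader to a later section on the dosing regimen "regarding lenalidomide dose adjustment for calculated creatinine clearance ≥ 30ml/min and < 60ml/min".
- **Section 6.4.1.** The 20 mg start applies "except patients with renal insufficiency, who will start at a lower dose, as above".

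The text that describes treatment reads differently:

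- **Synopsis, dosing regimen.** "Lenalidomide will be initiated at 20 mg daily, days 1-21 of a 28 day cycle".
- **Section 5.3.** "Lenalidomide will be started at 20 mg daily, days 1-21 of a 28 day cycle".
- **Opening line of section 6.** "All patients will receive the treatment regimen outlined below".
- **Section 6.1, Dosing regimen.** "The planned maximum dose of lenalidomide for investigation is 20 mg daily, days 1-21 of a 28 day cycle".

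The first three carry no renal exception. Section 6.1 calls 20 mg a maximum and does not mention renal function. Appendix VII requires the protocol coordinator to confirm each patient's dose level at registration and to fax it back within 3 hours.

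**The concern.** A patient with clearance of 30 to below 60 ml/min is eligible. Under the synopsis, section 5.3 and the opening of section 6, that patient starts at 20 mg. If the patient counts as having renal insufficiency, 6.4.1 says the start is lower. The reader is pointed forward from 5.4.1 and back from 6.4.1, and neither pointer reaches a dose.

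By the protocol's own account this bears on safety. Section 5.3.1.2 reports that, in healthy volunteers, about two-thirds of lenalidomide leaves the body unchanged in the urine, and section 4.1 names myelosuppression as the main dose-limiting toxicity. For the analysis, section 11.3 describes 30 patients treated at indicated dose levels, and for this subgroup no starting level is indicated.

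**Working it through.** No calculation applies. The check was to read every mention of renal function, creatinine clearance, starting dose and dosing regimen, and to ask whether any of them supplies the promised dose.

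| Place | Renal adjustment promised? | Adjusted starting dose stated? | Start or regimen given |
|---|---|---|---|
| Synopsis, dosing regimen | No | No | 20 mg, no exception |
| 5.3 | No | No | 20 mg, no exception |
| 5.4.1, criterion 8 | Yes, at 30 to below 60 ml/min | No, refers onward | None |
| 6, opening line | No | No | One regimen for all |
| 6.1, Dosing regimen | No | No | 20 mg as planned maximum |
| 6.4.1 | Yes, for renal insufficiency (undefined) | No, refers back | 20 mg with exception |
| 6.4.2, dose reduction steps | No | No | Level 0 is 20 mg; 15, 10 and 5 mg are levels -1 to -3 |
| Appendix III | No | No | Cockcroft-Gault formula only |
| Appendix VI | No | No | Link to the package insert only |

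Two places promise an adjustment and none states it.

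1. **The target of the pointer is present.** The dosing text in 6.1 is complete and readable. It covers the 20 mg maximum, timing, vomited and missed doses, overdose, anticoagulation and rituximab, and says nothing on creatinine clearance. The pages removed from the public file do not explain the gap: one precedes the contents list and the other falls within adverse event reporting, after 6.4.1.
2. **The lower doses in 6.4.2 do not fill the gap.** They come after the sentence that refers the reader upward, they serve the toxicity rules, and none is tied to a clearance range.
3. **The package insert is not invoked.** Neither 5.4.1 nor 6.4.1 refers to Appendix VI for this adjustment.
4. **The group is not fixed.** The range of 30 to below 60 ml/min appears only in 5.4.1. Section 6.4.1 uses a different term and does not link it to that range.
5. **The conflict.** For an eligible patient whom 6.4.1 treats as having renal insufficiency, a 20 mg start satisfies the synopsis, 5.3 and the opening of section 6 but not 6.4.1. A lower start satisfies 6.4.1 but departs from the synopsis and 5.3 as written.

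**The case against.** The best defence is that this is a general rule with an exception. Section 6.4.1 gives the 20 mg start and the renal carve-out in one sentence, and 6.1 speaks of a maximum, which leaves room for less. On that reading the synopsis and 5.3 are shorthand and the fault is a broken cross-reference. This stands in part: 6.1 does not itself contradict 6.4.1. It does not rescue the plan, because the exception has no content and the synopsis, 5.3 and the opening of section 6 do not signal that one exists.

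Some stronger readings are tempting, and the documents do not support them:

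- **That no lower dose appears at all.** Section 6.4.2 lists three. What is missing is a lower starting dose linked to renal function.
- **That these patients have no usable reduction steps.** The rules in 6.4.2 and 6.4.3 move one level down and work from any listed level. Only the entry point is undefined.
- **That each site will choose its own dose, blurring the response and toxicity rates.** Registration is central, and section 13.2 sends proposed exceptions to the coordinating investigator beforehand. A single ad hoc central decision is at least as likely. No effect on the rates can be quantified.
- **That a particular number of patients is affected.** An assumed share of 10% to 30% would give 30 × 0.10 = 3 to 30 × 0.30 = 9 patients. The documents give no share. The synopsis remark that most patients are elderly concerns non-Hodgkin's lymphoma generally, while eligibility here starts at age 18. Few or none might be affected.

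**Conclusion.** The concern holds as an internal inconsistency with a missing rule. Two sections promise a reduced starting dose for a group the protocol admits, and no section states it. The synopsis, section 5.3 and the opening of section 6 give these patients the same start or regimen as everyone else, in conflict with 6.4.1. The coordinator who must confirm a dose level has nothing to confirm it against.

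This conclusion rests on the text alone and on no assumed prevalence. Its clinical weight rests on the protocol's own excretion figure, which comes from healthy volunteers. It should be corrected because it concerns the starting dose of an investigational regimen and the remedy is small. It does not show that the planned response analysis is invalid.

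**What to change.** Before further registration, reconcile the synopsis, 5.3, 5.4.1 criterion 8, the opening of section 6, 6.1 and 6.4.1 by amendment. State in one place:

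- which patients count as having renal insufficiency, in terms of creatinine clearance;
- what starting level applies to them;
- where they enter the reduction table in 6.4.2.

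The other sections and the dose-level check in Appendix VII should then refer to that statement. The dose and the rule are for the sponsor and investigators to set, and none is proposed here.

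The cost is an amendment, which under section 12.1 needs Celgene review and IRB/EC approval, plus a change to the registration check. Listing the starting dose by renal group in the reports is optional and purely descriptive. If accrual has ended, that listing is the part that would still be useful.

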6.4.2 Instruction for Initiation of a New Cycle

A new course of treatment may begin on the scheduled Day 1 of a new cycle if:

- The ANC is $\geq 800/\mu L$;
- The platelet count is $\geq 50,000/\mu L$;
- Any lenalidomide or rituximab-related rash, allergic reaction/hypersensitivity or sinus bradycardia/ other cardiac arrhythmia adverse event that may have occurred has resolved to ≤ grade 1 severity;
- Any other lenalidomide-related adverse event that may have occurred has resolved to ≤ grade 2 severity.

If these conditions are not met on Day 1 of a new cycle, the subject will be evaluated weekly and a new cycle of lenalidomide will not be initiated until the toxicity has resolved as described above. If lenalidomide dosing was halted during the previous cycle and was restarted with a one-level dose reduction without requiring an interruption for the remainder of the cycle, then that reduced dose level will be initiated on Day 1 of the new cycle. If lenalidomide dosing was omitted for the remainder of the previous cycle or if the new cycle is delayed due to toxicity newly encountered on the scheduled Day 1, then the new cycle will be started with a one-level dose reduction.

Dose Reduction Steps

Dose level	Lenalidomide	Rituximab
0	20 mg (days 1-21/28 day cycle)	375 mg/m2 weekly x4
-1	15 mg (days 1-21/28 day cycle)	
-2	10 mg (days 1-21/28 day cycle)	
-3	5 mg (days 1-21/28 day cycle)	

6.4.3 Instructions for dose modifications or interruption of lenalidomide during a cycle.

Table 2: Dose Modification	on for Lenalidomide		
NCI CTC Toxicity Grade	Day 2-14 of Cycle	≥Day 15 of Cycle	
Grade 3 neutropenia associated with fever (temperature ≥ 38.5° C)	 Hold (interrupt dose). Follow CBC weekly. If neutropenia has resolved to ≤ grade 2 prior to Day 21, restart at next lower dose level and continue the cycle until Day 21. 	Omit lenalidomide for remainder of cycle .	
or Grade 4 neutropenia	NOTE: If neutropenia is the only toxicity for CSF may be used and the dose maintained for discretion		
Thrombocytopenia ≥Grade 4 (platelet count < 25,000/mm³)	 Hold (interrupt dose). Follow CBC weekly. If thrombocytopenia resolves to ≤ grade 2 prior to Day 21, restart at next lower dose level and continue the cycle until Day 21. 	Omit lenalidomide for remainder of cycle Hold ASA or other anticoagulant	
Thrombocytopenia, Grade 3 (platelet count 25,000 to 50,000/mm³)	Hold ASA or other anticoagulant	Hold ASA or other anticoagulant	
Non-blistering rash Grade 3	 If Grade 3 hold (interrupt) dose. Follow weekly. If the toxicity resolves to ≤ grade 1 prior to Day 21 restart at next lower dose level and continue the cycle until Day 21. 	Omit lenalidomide for remainder of cycle.	
Grade 4	Discontinue lenalidomide study drug.	Discontinue lenalidomide study drug.	
Desquamating (blistering) rash- any Grade	Discontinue lenalidomide study drug.	Discontinue lenalidomide study drug.	
Erythema multiforme≥ Grade 3	Discontinue lenalidomide study drug.	Discontinue lenalidomide study drug.	
Sinus bradycardia/ other cardiac arrhythmia Grade 2	 Hold (interrupt) dose. Follow at least weekly. If the toxicity resolves to ≤ grade 1 prior to Day 21 restart at next lower dose level and continue the cycle until Day 21. 	Omit lenalidomide for the remainder of the cycle.	
≥ Grade 3	Discontinue lenalidomide study drug.	Discontinue lenalidomide study drug.	

Table 2: Dose Modification for Lenalidomide			
NCI CTC Toxicity Grade	Day 2-14 of Cycle	≥Day 15 of Cycle	
Allergic reaction or hypersensitivity	ypersensitivity weekly. the cycle.		
Grade 2-3	• If the toxicity resolves to ≤ grade 1 prior to Day 21 restart at next lower dose level and continue the cycle until Day 21.		
Grade 4	Discontinue lenalidomide study drug.	Discontinue lenalidomide study drug	
Venous thrombosis/embolism ≥ Grade 3	Hold (interrupt) lenalidomide and start anticoagulation; restart lenalidomide at investigator's discretion (maintain dose level).	Omit lenalidomide for remainder of cycle. See Anticoagulation Consideration (Section 6.5.1.2)	
Hyperthyroidism or	 Omit lenalidomide for remainder of cycle, evaluate etiology, and initiate appropriate therapy. 	Omit lenalidomide for remainder of cycle, evaluate etiology, and initiate appropriate therapy.	
hypothyroidism	 See Instructions for Initiation of a New Cycle and reduce the dose of lenalidomide by 1 dose level. 	See Instructions for Initiation of a New Cycle and reduce the dose of lenalidomide by 1 dose level.	
	Hold (interrupt) lenalidomide dose. Follow at least weekly.	Omit lenalidomide for remainder of cycle.	
other non-hematologic toxicity ≥ Grade 3	• If the toxicity resolves to ≤ grade 2 prior to Day 21, restart lenalidomide at next lower dose level and continue the cycle through Day 21.	See Instructions for Initiation of a New Cycle and reduce the dose of lenalidomide by 1 dose level.	

